4.8 Evaluations by Visit

Visit 1: Screening Visit

- A. Review the study with the participant and obtain written informed consent and HIPAA authorization
- B. Assign a study ID
- C. Record demographic data
- D. Record medical history, including asthma questionnaires and history as appropriate
- E. Active viral infection screening per institution
- F. Record environmental history
- G. Record concomitant medications
- H. Collect urine for urinalysis, perform pregnancy testing (if applicable)
- I. Collect blood for CBC with differential, comprehensive chemistry panel (total of 15 ml) and optional (5 ml) for DNA / RNA testing
- J. Perform 12 lead electrocardiogram
- K. Review chest x-ray results if obtained, or provide requisition for chest x-ray if no historical is available within the last 12 months, and if subject opts in.
- L. Record vital signs, height, weight, and perform full physical examination
- M. Complete pulmonary function testing checklist
- N. Perform and record FeNO measurements
- O. Perform baseline spirometry with maximum bronchodilator reversibility testing.
- P. For participants with asthma, if reversibility criteria are not demonstrated, record historical MCT results, if obtained (acceptable test is one done per an NIH study protocol in the previous 5 years). If an acceptable historical MCT is not available, the participant will need to return for MCT (Visit 1A) prior to proceeding with the remainder of the procedures.
- Q. Perform Allergy Skin Testing
- R. Confirm eligibility criteria
- S. Schedule bronchoscopy, if possible
- T. Provide pre-bronchoscopy instructions, if proceeding with bronchoscopy
- U. Record adverse events

Visit 1A: Methacholine Challenge Testing (MCT)

For participants with asthma who did not meet bronchodilator reversibility criteria at Visit 1, this visit serves to confirm the diagnosis of asthma prior to proceeding with other study procedures. See below Schedule of Events for more details about accessibility of and opting out of methacholine challenge test.

- A. Confirm ongoing consent to participate
- B. Collect urine for pregnancy test if applicable
- C. Record vital signs, height and weight
- D. Complete MCT checklist
- E. Perform and record MCT
- F. Confirm eligibility criteria
- G. Complete any remaining procedures and forms from Visit 1
- H. Record adverse events

Visit 2: Research Bronchoscopy

See Schedule of Events for more details about accessibility of and opting out of bronchoscopy. Prior to Bronchoscopy, institutions may have subjects do a screening viral test. If active viral infection is present, bronchoscopy may be rescheduled.

- A. Confirm ongoing consent to participate
- B. Complete asthma questionnaires (if applicable)
- C. Obtain and record interval history
- D. Confirm eligibility criteria
- E. Record concomitant medications
- F. Perform urine pregnancy test if applicable.
- G. Record vital signs, height and weight, and perform abbreviated physical examination
- H. Complete pulmonary function testing checklist
- I. Perform pre-bronchoscopy spirometry
- J. Complete pre-bronchoscopy checklist to determine eligibility to proceed (may be done by phone up to 48 hours prior to visit)
- K. Obtain consent for bronchoscopy (clinical procedural consent)
- L. Complete bronchoscopy checklist
- M. Perform bronchoscopy with collection of airway pH and NOx measurements, airway gas samples, brushings, BAL and biopsies
- N. Perform post bronchoscopy spirometry
- O. Perform post bronchoscopy monitoring and assessment
- P. Provide post bronchoscopy instructions if participant meets discharge criteria
- Q. Record adverse events
- R. Perform telephone call in the evening to administer post bronchoscopy assessment

PC1, PC2, and PC3: Safety Phone Call (Day 1, 2, 3 after Visit 2)

- A. Record post bronchoscopy assessment
- B. Record adverse events

Visit 3: Inhaled GSNO Challenge Testing

- A. Confirm ongoing consent to participate
- B. Complete asthma questionnaires (if applicable)
- C. Obtain and record interval history
- D. Confirm eligibility criteria
- E. Record concomitant medications
- F. Record vital signs, height and weight, and perform abbreviated physical examination

- G. Perform urine pregnancy test if applicable
- H. Complete pulmonary function test procedure checklist
- I. Measure and record baseline FeNO
- J. Perform baseline spirometry (before GSNO administration)
- K. Administer 2.5 ml GSNO (10 mM) by inhalation
- L. Record FeNO measurements every 10 minutes after GSNO inhalation for 60 minutes. Monitor HR and pulse oximetry continuously, recording every 5 minutes. Measure BP and RR every 15 minutes.
- M. Perform final GSNO Challenge spirometry
- N. Perform maximum bronchodilator reversibility test
- O. Record Adverse Events
- P. Exit Review

5. SAFETY ASSESSMENTS

The monitoring in place for assessing the participant's responses will ensure that any untoward change in physiologic status is immediately known. As a result of the study design, individuals will be monitored on a case-by-case basis by the clinical research staff. The experimental design has each volunteer extensively monitored; any manner of medical intervention is immediately available and the appearance of any suspected untoward effect will result in cessation of protocol procedures if decided by the principal investigator.

Any member of the research team will report any unexpected event or problem and any adverse event, either serious or non-serious, to the principal investigator immediately upon discovery. The principal investigator will then proceed to report the event within the specified timeframes mandated by the UHMC IRB and the Data and Safety Monitoring Board (DSMB).

There is a DSMB providing oversight to this study. It functions as an independent medical monitor and adverse event (AE) review adjudication board; it will have the responsibility to review all AEs

and any other duties that the UHCMC IRB requires. In addition, the DSMB will provide feedback and expertise in determining study continuance as it reviews any serious AE.

5.1 Adverse Events and Severity Grading

The UHCMC IRB and the FDA have well-established policies (and means) for prompt reporting of AEs and unanticipated problems involving risk to participants or others and these policies will be strictly followed.

Adverse Events

An AE is any untoward medical occurrence associated with the use of a drug in humans, whether or not considered drug related. For this study, AEs will be recorded from the time of consent through Study Visit 3. Unexpected events are defined as any adverse event, the specificity or severity of which is not consistent with the risk information described in the general investigative plan (i.e., research plan) or elsewhere in the current application including the consent form. The Investigator or Research Coordinator will probe, via discussion with the participant, for the occurrence of AEs during each participant visit and record the information in the site's source documents. AEs will be described by duration (start and stop dates and times), severity, outcome, treatment and relation to investigational product, or if unrelated, the cause.

AE Severity

The National Cancer Institute's (NCI) Common Terminology Criteria for Adverse Events (CTCAE) Version 4.0, summarized in Table 4 below, should be used to assess and grade AE severity, including laboratory abnormalities judged to be clinically significant. It should be pointed out that the term "severe" is a measure of intensity and that a severe AE is not necessarily serious.

Table 4. AE Severity Grading (based on NCI's CTCAE Version 4.0)

Severity (Toxicity Grade)	Description
Grade 1	Mild; asymptomatic or mild symptoms; clinical or diagnostic observations only; intervention not indicated.
Grade 2	Moderate; minimal, local or noninvasive intervention indicated; limiting age-appropriate instrumental ADL*.
Grade 3	Severe or medically significant but not immediately life-threatening; hospitalization or prolongation of hospitalization indicated; disabling; limiting self-care ADL**.
Grade 4	Life-threatening consequences; urgent intervention indicated.
Grade 5	Death related to AE.

A Semi-colon indicates 'or' within the description of the grade. Activities of Daily Living (ADL)

* Instrumental ADL refer to preparing meals, shopping for groceries or clothes, using the telephone, managing money, etc.

** Self-care ADL refer to bathing, dressing and undressing, feeding self, using the toilet, taking medications, and not bedridden.

5.2 AE Relationship to Investigational Product

The relationship of an AE to the study drug should be assessed using the following the guidelines in Table 5.

Table 5. AE Relationship to Investigational Product

Relationship to Drug	Comment
----------------------	---------

Definitely	Previously known toxicity of agent; or an event that follows a reasonable temporal sequence from administration of the drug; that follows a known or expected response pattern to the suspected drug; that is confirmed by stopping or reducing the dosage of the drug; and that is not explained by any other reasonable hypothesis.
Probably	An event that follows a reasonable temporal sequence from administration of the drug; that follows a known or expected response pattern to the suspected drug; that is confirmed by stopping or reducing the dosage of the drug; and that is unlikely to be explained by the known characteristics of the participant's clinical state or by other interventions.
Possibly	An event that follows a reasonable temporal sequence from administration of the drug; that follows a known or expected response pattern to that suspected drug; but that could readily have been produced by a number of other factors.
Unrelated	An event that can be determined with certainty to have no relationship to the investigational product.

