During regular times, urine collection will be completed in clinical research center. During viral infection crisis restrictions, urine collection may be completed in the clinical research center (or in-tent option for IU), or at an alternative outpatient facility with results sent to study team.

GSNO Challenge Testing GSNO is to be manufactured under Good Manufacturing Practice conditions by an appropriate commercial entity (Ricerca Biosciences) under the IND held by [name]. One dose of 2.5 mL 10 mM GSNO in normal saline, prepared by a qualified sterile compounding pharmacy, will be administered for this protocol as we have previously published (14). Study drug will be stored and dispensed by a local, qualified sterile compounding pharmacy.

Results to date from clinical testing of GSNO have been positive with no identified toxicities or drug-related adverse events (14). Nonetheless, out of an abundance of caution, participants scheduled for GSNO treatment will be required to have normal vital signs, pulse oximetry >90%. All participants must be free from an intercurrent illness within the previous 14 days. Participants with asthma must be free from an exacerbation of asthma in the previous 14 days, defined as increased asthma symptoms requiring an increase in short acting bronchodilator use above that established at the baseline visit for more than 24 hours or use of systemic corticosteroids.

Baseline FeNO and spirometry measurement will be recorded. One unit dose of GSNO is administered via standard nebulization. Following administration of inhaled GSNO, participants will be monitored for signs of bronchospasm (e.g., wheeze, cough, dyspnea, etc.). Serial FeNO measurements will be made every 10 minutes for 60 minutes. Heart rate and pulse oximetry will be monitored continuously. Other vital signs will be monitored every 15 minutes. Spirometry will be performed at the conclusion of the FeNO measurements. A study physician will be available to evaluate participants complaining of cough, wheezing, dyspnea, or with a decline in FEV₁ of 10% or greater from pre-challenge baseline. Inhaled beta-agonist may be given at the study physician's discretion.

During regular times and during viral infection crisis restrictions, GSNO challenge testing may only be completed in clinical research center (or in-tent option for IU).

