7.2 Stopping Rules

The risks associated with this trial are low but not zero. Investigators will report all serious adverse events within 24 hours of learning of them to the DSMB as described in Section 5.3. The DSMB will review SAEs within 3 business days. All study procedures for the affected participant will be stopped until the DSMB is able to review the event and recommend changes to the protocol if needed. Any SAE deemed by the investigator to be probably or definitely related to study drug or bronchoscopy will result in stopping of all study procedures other than safety monitoring for all active participants until DSMB review is complete. A DSMB review will also be triggered if two or more patients have a greater than or equal to 15% reduction in FEV₁ following inhaled glycine administration that does not return to baseline.

DSMB recommendations that are voted on and passed are transmitted in writing to the study PI and the Program Director, within three (3) working days, or less if considered urgent, of the meeting/call at which the recommendation was formulated and passed.

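### On the wording of Table 5, a serious event that begins after the single GSNO dose is complete cannot reach the grades that trigger the study-wide halt in section 7.2

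*Combined protocol and SAP*

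**What the plan says.** Section 5.2 opens: "The relationship of an AE to the study drug should be assessed using the following the guidelines in Table 5". The table has four grades.

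- *Definitely* has two routes. It begins "Previously known toxicity of agent; or an event that follows a reasonable temporal sequence from administration of the drug". The second route then adds further conditions, including "that follows a known or expected response pattern to the suspected drug; that is confirmed by stopping or reducing the dosage of the drug".
- *Probably* asks for a plausible time sequence, a known or expected pattern, and the clause "that is confirmed by stopping or reducing the dosage of the drug; and that is unlikely to be explained by the known characteristics", which refers to the participant's own condition.
- *Possibly* asks for the time sequence and the pattern, and that other factors could readily explain the event. It has no condition about stopping the drug.
- *Unrelated* requires certainty that there is no relationship.

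Section 4.7.2 gives the exposure as "One dose of 2.5 mL 10 mM GSNO in normal saline", nebulised, and section 4.8 lists one administration at Visit 3. Section 4.7.2 also describes clinical results to date as "positive with no identified toxicities or drug-related adverse events".

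Section 7.2 stops all procedures except safety monitoring, for all active participants, on "Any SAE deemed by the investigator to be probably or definitely related to study drug or bronchoscopy", until the DSMB has completed its review.

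**The concern.** Confirmation by stopping or reducing a drug (dechallenge) suits repeated dosing. Here it is a condition for the grades that control the study-wide halt, yet each participant has a single exposure that is over within one visit. If the table is applied as written, the automatic pause depends on a condition that most post-dose events cannot meet by construction.

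The people at stake are those not yet dosed. The plan is for 50 participants with asthma and 10 healthy volunteers, 60 in all, one dose each. Stopping procedures for the affected person comes after that person's only dose, normally at the last visit, and does not by itself keep anyone else from being dosed before the DSMB has reviewed the event. A halt that works only when an investigator overrides the protocol's own definitions may also be applied differently at the two sites.

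The table has a second gap. Section 5.1 asks that every adverse event be described by its relation to the product, but there is no grade between *Possibly*, which needs a pattern, and *Unrelated*, which needs certainty.

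**Working it through.** The plan gives no figure on this point, so the check sets the sections side by side.

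**Inputs**

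1. Number of doses: one (sections 4.7.2 and 4.8, Visit 3).
2. Delivery: by nebuliser, hence over some time; the duration is not stated (section 4.7.2).
3. Known toxicity: none identified (section 4.7.2).
4. Effects that could count as expected: section 5.6 lists hypotension, dizziness, nausea, fatigue, blurred vision and hemoptysis as theoretical risks. Section 4.7.2 has participants watched for bronchospasm.
5. Grades that halt the study: *Probably* and *Definitely* (section 7.2).

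**How the table reads.** The condition lists for *Probably* and the second route to *Definitely* each close with *and*, so their conditions are cumulative. The note that a semicolon means *or* belongs to Table 4, on severity, and is not attached to Table 5.

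**Each grade against three kinds of serious event**

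| Table 5 grade | Expected kind, starts during nebulisation | Expected kind, starts after the dose | New kind, not excluded with certainty |
|---|---|---|---|
| *Definitely*, known toxicity | Not met: none identified | Not met: none identified | Not met: none identified |
| *Definitely*, second route | Can be met: nebuliser can be stopped | Not met: no dosage left | Not met: no pattern |
| *Probably* | Can be met: nebuliser can be stopped | Not met: no dosage left | Not met: no pattern |
| *Possibly* | Can be met | Can be met, if other factors could readily explain it | Not met: no pattern |
| *Unrelated* | Only with certainty | Only with certainty | Not met |
| Halting grades open | 2 of 2 | 0 of 2 | 0 of 2 |

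In the middle column the highest grade available is *Possibly*, which does not trigger the halt. In the last column 0 of 4 grades apply, whenever the event starts.

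**Whether another rule fills the gap.** Section 7.2 also triggers a DSMB review when two or more patients have an FEV1 fall of at least 15% that does not return to baseline. That trigger names inhaled glycine, whereas this protocol gives GSNO, so as worded it is not a clear backstop. Under section 5.3, collection of serious events ends at Visit 3, the visit at which GSNO is given.

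**The case against.** The strongest reply is that the plan does not leave participants unprotected and that Table 5 is not a mechanical gate. Much of this stands.

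- Under sections 5.3 and 7.2, every serious event goes to the DSMB within 24 hours whether or not it is related. The affected participant's procedures stop, and the DSMB reviews within 3 business days. Section 5 lets the principal investigator stop procedures for a suspected effect and has the DSMB advise on continuing the study. What is impaired is one automatic, immediate, study-wide pause, not every route to stopping.
- Table 5 is offered as guidelines, and section 7.2 turns on what the investigator deems. An investigator may grade a post-dose event *Probably* despite the table. That is true, but the halt then works by setting the definitions aside.
- A reader might infer that the halt can never fire for GSNO. The documents do not support that. Nebulisation can be interrupted, so an event of expected kind during it can satisfy the condition. A toxicity may also become known during the study, which would open the first route to *Definitely*.
- A reader might infer that every related grade needs dechallenge, or that the lack of known toxicity defeats the pattern condition. Neither follows: *Possibly* has no dechallenge condition, and the pattern may be known **or** expected, for which sections 5.6 and 4.7.2 supply candidates.
- A reader might infer that an unexpected event can never be graded related. Section 5.1 says: "Unexpected events are defined as any adverse event, the specificity or severity of which is not consistent with the risk information". An effect of a listed kind that is merely more severe than described is unexpected and can still follow an expected pattern. The gap concerns only reactions of a new kind.

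**Conclusion.** The point holds in a bounded form. For a serious event that starts after the GSNO dose is complete, neither halting grade can literally be met, so the automatic halt in section 7.2 is effectively unavailable unless the investigator departs from Table 5. For an event of expected kind during nebulisation, both halting grades remain reachable. Independently, a reaction that follows no known or expected pattern and cannot be excluded with certainty has no grade at all.

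This rests on three assumptions: the table is followed as written, its conditions are cumulative, and the statement in section 4.7.2 that no toxicity has been identified remains true. It does not extend to the bronchoscopy half of the trigger, because Table 5 is worded for the drug. It is a safety rule that misfires on its own definitions, and it should be corrected. It does not show that serious GSNO events would escape review.

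**What to change.** The sponsor and DSMB should reconcile three places: Table 5 in section 5.2, the single-dose administration in sections 4.7.2 and 4.8, and the trigger in section 7.2. The reconciled text should achieve two things:

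1. The grades on which the study-wide halt depends can be reached for an event that begins after a completed dose.
2. Every event that cannot be excluded as drug-related has a grade, so that the relation section 5.1 asks for can be recorded.

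The causality criteria that achieve this, and the halt threshold itself, are for the sponsor and DSMB to decide. In the same pass they should reconcile the reference to inhaled glycine in the FEV1 review trigger with the agent that this protocol gives.

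The cost is protocol wording and the matching help text on the case report form. The downside is small: a few more events may be graded related, and some of these may pause the study.

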5.3 Serious Adverse Events (SAEs) and Reporting

An SAE is defined as any AE occurring at any dose that results in any of the following outcomes:

- Death
- A life-threatening adverse experience
- Inpatient hospitalization or prolongation of existing hospitalization
- A persistent or significant disability/incapacity
- A congenital anomaly/birth defect

Other important medical events may also be considered an SAE when, based on appropriate medical judgment, they jeopardize the participant or require intervention to prevent one of the outcomes listed.

SAE Reporting

All SAEs will be documented (whether or not related to investigational product) on a SAE Report Form. The collection period for all SAEs will begin after informed consent is obtained and end at Study Visit 3.

All SAEs will be reported and reviewed by the investigator and sent to the DSMB, within 24 hours of learning of the event.

Study staff will notify the DSMB of additional information or follow-up to an initial SAE Report as soon as relevant information is available. Follow-up information is reported on an SAE Report Form.

DSMB recommendations that are voted on and passed are transmitted in writing to the study PI and the Program Director, within three (3) working days, or less if considered urgent, of the meeting/call at which the recommendation was formulated and passed.

The investigator will report all SAEs to the UHCMC IRB, in accordance with the UHCMC standard operating procedures and policies. SAEs will be reported to the FDA in accordance with 21 CFR 312.32.

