Methacholine Methacholine Challenge Test can only be completed in the clinical setting; if a clinical setting is not available during crisis restrictions, subjects may be forced to opt out. If a clinical setting is available, but a subject does not feel comfortable entering a clinical building due to viral infection risks, they may opt out of the Methacholine Challenge Test.

The Methacholine Challenge Test serves as a tool to maximize the inclusion of subjects – if a subject does not have a diagnosis of asthma, they would take the Methacholine Challenge to confirm or rule out eligibility based on Methacholine Challenge Test results. It is possible that a subject may need the Methacholine Challenge Test to be considered eligible, but will not be able to complete the challenge test due to clinical setting availability or due to subjects' level of comfort with the clinical setting, and may therefore be considered ineligible because of not being able to complete it. The study team anticipates this will not be a common occurrence.

Chest X-Ray During viral infection crisis restrictions, a chest x-ray may be completed at an alternative radiology outpatient facility if results can be sufficiently provided to the study team, or it may be completed at the site's radiology facility. If the subject is uncomfortable entering a radiology facility due to viral infection risks, they may choose to opt out of completing the chest x-ray part of the study.

Bronchoscopy Bronchoscopies may only be completed at the hospital. If research bronchoscopies are not permitted at the institution, a subject may choose to defer the bronchoscopy for up to 1 year, or may be forced to opt out due to the availability. If research bronchoscopies are permitted at the institutions, but the subject does not feel comfortable entering the bronchoscopy suite, they may choose to defer the bronchoscopy for up to 1 year or may choose to opt out of the bronchoscopy entirely. If a subject chooses or is forced to opt out of the bronchoscopy, their study data set may be considered complete without bronchoscopy; it is possible that only a subset of subjects may complete bronchoscopies and therefore have bronchoscopy data. Additionally, if a subject is allergic to anesthetic medications (e.g., lidocaine) and they opt out of the bronchoscopy, they may continue in the study.

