4.7 Description of Procedures and Evaluations

4.7.1 Description of Study Visits

There are three to four in-person visit opportunities, two possible unscheduled visits, and three phone call assessments (Safety Phone Calls). Details about procedures at each visit are found below.

1. Consent, screening, and characterization (V1)
2. Methacholine Challenge Test (MCT) (V1A) – only for participants with asthma who do not demonstrate bronchodilator reversibility and do not have historical MCT results available
3. Research bronchoscopy (V2)
4. Safety phone calls (PC1, PC2, PC3)
5. Inhaled GSNO challenge testing (V3)
6. Unscheduled visits are being included in case the participant needs to return to complete study activities (e.g., the participant forgot to withhold allergy medications on the day of allergy testing).

The following guidelines should be used for scheduling participants:

- Visit 1 = Day 0
- Each visit must be completed within 56 days of the previous visit
- Each visit must be at least 1 day apart
 - **Exceptions:** participants who have an MCT must wait at least 2 days before returning for V2 (bronchoscopy); participants who have had a bronchoscopy must wait 7 days before completing the next study visit (whether for the same study or if crossing over)

Significant health findings found during the study will be reported to the participant to further discuss with their regular doctor.

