For participants with asthma, methylprednisolone IV may be administered following the procedure at the investigator's discretion. Antipyretics may also be administered to all participants at standard doses per hospital procedures. Clinical documentation of all medications administered (including conscious sedation medications) will serve as source documentation.

Assessment for the presence of hospitalization indicators should be made (Table 3). If any are present, the participant should be hospitalized overnight. The development of hospitalization indicators and subsequent hospitalization, *does* constitute a serious adverse event.

Post bronchoscopy spirometry should be measured a minimum of 1 hour after the procedure is ended. The participant may be discharged following the minimum recovery time if FEV₁ reaches $\geq 85\%$ of that observed in the pre albuterol spirometry obtained prior to bronchoscopy.

Post bronchoscopy assessment should be administered after the procedure, by telephone the evening of the procedure, and by telephone daily for the following 3 days.

Table 3. Indications for overnight hospitalization following bronchoscopy

Failure of FEV ₁ after bronchodilator administration to return to within 15% of pre-bronchodilation FEV ₁ at end of the monitoring time
Persistent hypoxia <90% at end of monitoring time
Persistent tachycardia (HR 130 bpm) at end of monitoring time
Unexpected mental status changes during or after the procedure
Significant hemoptysis (> 50 mL)
Requirement for bronchodilator every 2 hours on more than 3 occasions
Significant distressing cough beyond 2 hours after completion of the procedure
Investigator discretion

Prior to the procedure, the participant must identify a responsible adult to whom the participant will be discharged following the procedure. Research and bronchoscopy staff will review standard post bronchoscopy instructions with the participant and the responsible adult.

Despite appropriate selection, preparation, procedural technique, post bronchoscopy monitoring, and physiologic assessment prior to discharge, it is possible that participants occasionally will require urgent care following discharge from the procedure unit.

Infrastructure should be in place to recognize the need for, and to facilitate, such care should the need arise.

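### AE and SAE collection ends at Visit 3, where the only GSNO dose is given, and no later contact is planned to find events that start after discharge

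*Combined protocol and SAP*

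**What the plan says.** **Collection period.** For adverse events, Section 5.1 states that "AEs will be recorded from the time of consent through Study Visit 3". For serious events, Section 5.3 states that the collection period will "begin after informed consent is obtained and end at Study Visit 3".

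**Drug exposure.** Section 4.7.2 (GSNO Challenge Testing) specifies "One dose of 2.5 mL 10 mM GSNO in normal saline". The Visit 3 list in Section 4.8 places it there: "Administer 2.5 ml GSNO (10 mM) by inhalation". After dosing, that list runs through 60 minutes of FeNO, final spirometry, the maximum bronchodilator reversibility test, AE recording and an exit review. Table 1 in Section 4.6 has no column after Visit 3.

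**Bronchoscopy.** Section 4.7.2 F asks for an assessment after the procedure, a telephone call that evening, and further assessment "by telephone daily for the following 3 days". Table 1 and Section 4.8 list AE recording at Visit 2 and at each of these three daily calls (PC1 to PC3).

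**Deferral.** Under viral-crisis restrictions, Section 4.6 says of participants who are uncomfortable entering the bronchoscopy suite that "they may choose to defer the bronchoscopy for up to 1 year". The same option applies where the institution does not permit research bronchoscopies.

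**The concern.** The only investigational drug in the study is given at the visit that closes safety collection. Apart from the remaining hours of that visit, everything collected on adverse events precedes exposure to GSNO. The procedure that is not the investigational product has planned follow-up after discharge, and the drug has none.

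Two things depend on this. One is what the study can say about GSNO safety: a clean record would describe events that began before the participant left the clinic, and nothing later. The other is the stopping rule in Section 7.2, which suspends procedures for all active participants when an SAE is judged probably or definitely related to study drug or bronchoscopy. That rule can act only on events that come to the study team's notice.

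The deferral option raises a separate question. If a deferred bronchoscopy took place after Visit 3, the formal collection period would already be over when the more invasive procedure was done.

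**Working it through.** The protocol gives no figure to reproduce here. The check sets its sections side by side and adds the intervals it states.

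**1. Overlap of window and exposure.** Sections 5.1 and 5.3 end the window at Visit 3. Sections 4.7.1 and 4.8 make Visit 3 the GSNO challenge, and Section 4.7.2 gives one dose. Post-drug time inside the window is therefore the remainder of Visit 3 only.

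**2. Length of that remainder.** Inputs are FeNO for 60 minutes (Section 4.8), final spirometry of unstated length *s* (Section 4.8), and three reversibility steps of 15 minutes (Section 4.7.2, Lung function testing, B).

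T = 60 + *s* + 3 × 15 = 105 + *s* minutes, so at least about 105 minutes. The last 45 of these follow albuterol (4 + 2 + 2 = 8 puffs).

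**3. Comparison with bronchoscopy in the default visit order.**

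| | After GSNO | After bronchoscopy |
|---|---|---|
| On-site time | at least about 105 min | at least 1 h, or 2 h if sedated |
| Call the same evening | none | 1 |
| Daily calls afterwards | 0 | 3 |
| Window still open after leaving | no | yes, until Visit 3, at least 7 days later |

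**4. Whether another provision reopens the window.**
- Section 5.5 leaves follow-up to case-by-case direction and sets no period or contact for finding new events.
- The follow-up reports in Section 5.3 concern SAEs already reported.
- The unscheduled visits in Section 4.7.1 are for completing study activities.
- The start of Section 5 has the team report events on discovery, which presupposes that someone learns of them.

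None of these supplies active ascertainment after Visit 3.

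**5. Deferred bronchoscopy against the visit windows.** Section 4.7.1 requires each visit within 56 days of the previous one, and its listed exceptions concern minimum gaps only. Assume that the year (365 days) is counted from Visit 1.
- Default order: Visit 2 is due within 56 days of Visit 1, or 2 × 56 = 112 days if Visit 1A intervenes.
- Visit 3 before Visit 2: the latest day for Visit 2 is 2 × 56 = 112, or 3 × 56 = 168 with Visit 1A.

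A full year's deferral fits neither order. Section 3 has participants return for GSNO after bronchoscopy, and no section says that Visit 3 goes ahead while a bronchoscopy is deferred. If it did, Table 1 and Section 4.8 would still call for AE recording at Visit 2 and PC1 to PC3. Section 4.7.2 F would still ask for all events to be documented, but it refers reporting to Section 5, where the window has closed.

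**6. What a clean record would mean.** Assume all 60 planned participants are dosed and none has an event. The one-sided 95% upper bound is 1 − 0.05^(1/60) = 4.9% (rule of three: 3/60 = 5%). It applies only to events that begin before the participant leaves Visit 3.

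**The case against.** The strongest case against has four parts.

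- **Late events are not barred from reporting.** Section 5 has any team member report any adverse event on discovery. Section 5.3 sends SAEs to the DSMB within 24 hours of learning of them, and to the IRB and FDA. Those sentences do not repeat the Visit 3 limit. This stands. A reader might infer that a late SAE would reach neither the DSMB nor the FDA, but the documents do not support that. They show only that no planned contact would find it and that it lies outside the stated collection period.
- **Bronchoscopy events are recorded anyway.** A reader might infer that events after a deferred bronchoscopy go uncaptured. The documents do not say that such a bronchoscopy follows Visit 3, and the remark in Section 3 about visits out of order belongs to the crossover from Project 2. Deferral is limited to crisis restrictions. Even in the reversed order, AE recording is listed at Visit 2 and the three calls. What remains is a conditional conflict of wording.
- **Observation after GSNO exceeds the hour of FeNO.** This stands, and the figure to use is at least about 105 minutes. Nor can it be set against 4 to 12 weeks of collection for everyone: crossover participants under Table 1's footnote have modified screening and take part only in Visit 3.
- **The harm is partly hypothetical.** Section 5.6 lists theoretical GSNO risks and does not name delayed exacerbation among them. GSNO safety is not a stated objective, and closer follow-up after an invasive, possibly sedated procedure is a reasonable risk-based choice. That explains more contact after bronchoscopy. It does not explain none after the investigational drug.

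**Conclusion.** The point holds for GSNO. Safety collection closes at the visit where the single dose is given. Planned post-dose observation is at least about 105 minutes, and scheduled contact after discharge is zero. A new event that begins later is outside the window and may not trigger the Section 7.2 rule on drug-related SAEs unless someone reports it spontaneously.

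On bronchoscopy the conclusion is narrower. The one-year deferral does not fit the 56-day rule, and if the procedure came after Visit 3, Section 5 would conflict with the AE recording listed for Visit 2 and PC1 to PC3.

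This rests on reading Sections 5.1 and 5.3 literally and on Table 1 being the full schedule of contacts. How often events would start after discharge cannot be derived from the documents. No primary endpoint or power figure is affected. I grade this as should-fix: a real gap in safety capture that is cheap to close.

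**What to change.** 1. In Sections 5.1 and 5.3, define the end of AE and SAE collection relative to the last study intervention, GSNO or bronchoscopy, whichever is later, so that it holds for any visit order.
2. Add a telephone contact after Visit 3 with AE recording, entered in Table 1 and Section 4.8. The sponsor and DSMB should set its timing.
3. State in Section 5.3 that SAEs reported spontaneously after collection ends are still handled under the reporting rules.
4. Reconcile the deferral text in Section 4.6 with the 56-day rule in Section 4.7.1 and the visit order in Section 3, and align Section 4.7.2 F with Section 5. Which visit rule should prevail is for the sponsor to decide.

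The cost is one short call per participant by existing staff (60 calls if all 50 + 10 planned participants are dosed), plus amendment wording.
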